9. CRITERIA FOR INTERVENTION DISCONTINUATION

The PI & Co-PI can discontinue study intervention(s) based on their clinical judgment & patient's best interest. All the data that needs to be entered in the Case Report Form (CRF) will be collected and data from discontinued study participants will be factored in in the analysis.

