10. STATISTICAL CONSIDERATIONS

Design:

The clinical trial will be conducted under a common umbrella protocol developed by the primary site (UTH) with the intention of combining data from all satellite centers for analysis. Each investigational site will give utmost importance to follow the study protocol to maintain consistency in study execution at all centers. Patients will be randomly assigned to 3 treatment groups in a 1:1:1 allocation ratio. The three therapeutic regimens to be considered are:

Group 1: nicardipine (Cardene) 5 mg per circulation in 25 mL of 5% Dextrose,

Group 2: verapamil 10 mg per circulation in 10 mL saline

Group 3: Cocktail agents: 5 mg in 25 mL 5% Dextrose + verapamil 10 mg in 10 mL saline + nitroglycerin 200 mcg in 4 cc of D5W per circulation.

A maximum of 330 subjects, 110 per treatment arm, will be randomized. The trial includes interim analyses that may reduce the maximal sample size if clear differences emerge among the arms during the conduct of the trial.

Interim Analyses:

Interim analyses will be performed to allow for discontinuing enrollment to treatment arms due to futility. After approximately 90 subjects have been randomized, 30 per arm, interim analyses will begin at the next quarterly Data and Safety Monitoring Board (DSMB) meeting. Subsequent interim analyses will be performed to coincide with DSMB meetings, which will occur after 40 subjects, 70 subjects, 110 subjects, 165 subjects, and 248 subjects have completed the study, and at the conclusion of the study (330 subjects).

At each interim analysis, an Analysis of Variance (ANOVA) will be performed to compare the PIIR results across treatment arms. If the overall treatment effect is significant with a p-value<0.05, then pairwise treatment comparisons will be performed. If any pairwise comparison is significant at a Tukey's adjusted two-sided p-value of 0.02 (p< 0.02), the poor performing arm will be dropped from the randomization scheme. If multiple arms are dropped and only one treatment arm remains open for randomization, that arm will be declared as best, and the clinical trial will end. Pairwise comparisons will only be performed if the overall treatment effect in the ANOVA is significant.

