A maximum of 110 subjects will be randomized to each treatment arm, for a total sample size of 330. If an arm or arms are dropped early, the final sample size will be less than 330. For example, suppose an interim analysis is performed after 70 subjects are randomized to the 3 treatment arms (total sample size 210). Suppose further, at the interim analysis one arm is dropped, and the remaining two arms continue to enroll to completion. The final sample size will be 290, i.e., 70 subjects in the dropped treatment arm, and 110 in each of the remaining treatment arms.

Enrollment will continue while the interim analyses are performed

Final Analyses:

All patients will be included in analyses utilizing the Intent-to-Treat approach that includes all subjects randomized in their randomized treatment arm regardless of treatment received.

At the final analysis, the primary outcome measure, PIIR will be compared between treatment arms using an ANOVA model. All data will be used in the final analysis, including any arms that may have been dropped from the randomization. If the overall treatment effect in the ANOVA model is significant at the two-sided, 5% level, then pairwise comparisons among treatment arms will be conducted using Tukey's adjusted p-values with p<0.0330 declared as statistically significant. This value controls global type I error (mistakenly claiming any pairwise difference when all treatments are equal) accounting for 6 interim analyses at the anticipated accrual rate of 2 years. If accrual significantly deviates from the anticipated accrual rate, further trial simulations will be conducted to determine an appropriate adjustment for the actual number of interim analyses conducted.

Descriptive statistics, means, medians, and standard deviations, will be reported for PIIR in each treatment arm. The two-sided 95% confidence interval will also be presented for the PIIR in each treatment arm.

The key secondary outcome, mRS (Modified Rankin Scale) at 3-months post-treatment, will be summarized by treatment arm by reporting the counts and proportions in each mRS category. Comparisons among treatment groups will be made using a Chi-square test.

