Additional secondary outcomes include SAE (severe adverse event) occurrences and the rate of treatment failure with balloon angioplasty. These outcomes will be summarized descriptively by presenting rates and proportions. Exploratory analyses comparing outcomes between treatment arms will be made using a Chi-square test.

Additional exploratory multivariable linear regression models will be created for the PIIR outcome, adjusting for treatment groups and additional baseline factors.

The analyses for the secondary outcomes are considered exploratory and no adjustments for the multiple tests and multiple comparisons will be made. Results will be interpreted cautiously understanding the some results may be significant at the 5% level due to chance alone.

Sample Size Justification:

Simulations were performed to estimate the power of the study for the primary outcome measure, PIIR, with a maximum sample size of 330 (110 per treatment arm) and the interim analyses for possible early arm dropping. A range of scenarios of PIIR were examined; the key scenarios used to power the trial are presented in Table 2.

Table 2.

Scenario	Treatment Arm 1: Nicardipine (N)	Treatment Arm 2: Verapamil (V)	Treatment Arm 3: Combination (C)
Combo 20	0.10	0.10	0.30
Mixed 1530	0.10	0.15	0.30

Note that the scenarios are both in favor of Verapamil over Nicardipine, but the results are symmetric if Nicardipine and Verapamil were reversed.

The trial will make every pairwise comparison:

- N versus V
- N versus C
- V versus C

The simulations focused on the V>N, C>N, and C>V comparisons. The following table presents the expected (mean) sample size and probability that the combination treatment regimen is better than the verapamil regimen, i.e., Pr(C>V), the main comparison of interest. Power is defined as the probability of identifying the superiority of the best dose over the other two doses.

Table 3.

Scenario	Expected N	Power Pr(C>V)
Combo 20	177	0.95
Mixed 1530	211	0.77

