In order to ensure patient safety and integrity of data collection, data and safety monitoring during this trial will include both internal and external mechanisms. The PI has developed an internal monitoring system, which will be implemented after each enrolled patient and on a monthly basis at the host site, University of Texas Health Science Center Houston. The study team will perform internal monitoring. In addition, on a yearly basis, a monitor will be asked to review study and safety data for all participating centers. Monitoring of participating centers will occur on a yearly basis, or following the completion of the study for each additional two subjects at each center, whichever occurs first. Monitoring may occur in person, or remote. Lastly, the Data and Safety Monitoring Board will independently review the accumulating data, assess the risk to benefit ratio, and can consider halting the trial if the risk to benefit ratio is deemed unacceptable. The external monitor and the DSMB will also monitor protocol compliance, safety, and onschedule study progress.

11. DATA COLLECTION, SITE MONITORING AND ADVERSE EVENT REPORTING

Data collection: detailed clinical information will be gathered using an established method approved by UT Health for abstracting information from electronic database and by the approved established method at each participating site.

Each participating center will use REDCap data software an online secure web application to enter the data in the central REDCap database managed by UT-Houston.

All the radiographic images will be evaluated and analyzed by a single CORE LAB (at The University of California – Los Angeles) centrally in blind fashion. The radiographic images will be submitted via VPN with security and with federal Health Insurance Portability and Accountability Act (HIPPA) compliance.

The patient's demographics (gender, age, race, BMI, co-morbidity, tobacco use, cocaine/illicit drug use history), aneurysm treatment modality, days after the SAH and aneurysm treatment, vasodilator(s) used (Group #) and numbers of the treatment sessions will be submitted via REDCap. Summaries will be provided quarterly to the DSMB members.

Records to Be Kept: All patient data will be de-identified and CRFs will be stored on password protected cloud drive

Data and Safety Monitoring Plan & Quality Assurance:

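### SAEs are compared only by randomised arm; adding a table by regimen received would guard against a usually small dilution of drug-related differences

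*Combined protocol and SAP*

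**What the plan says.** The Final Analyses part of Section 10 applies intent-to-treat to every patient, in a form that "includes all subjects randomized in their randomized treatment arm regardless of treatment received". This is the only analysis population in the document.

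The same part then names the harm outcome: "Additional secondary outcomes include SAE (severe adverse event) occurrences and the rate of treatment failure with balloon angioplasty". On the method it says "These outcomes will be summarized descriptively by presenting rates and proportions", followed by "Exploratory analyses comparing outcomes between treatment arms will be made using a Chi-square test". Secondary analyses are labelled exploratory and are not adjusted for multiplicity. Non-serious adverse events have no stated analysis.

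Section 9 adds that "data from discontinued study participants will be factored in in the analysis", without saying whether such patients are grouped by assignment or by treatment received. No safety, as-treated or any-infusion population appears anywhere.

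Three sections bear on whether a randomised patient might go uninfused:

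- Section 4 (Randomization): the physician learns the arm only once the diagnostic angiogram has confirmed that drug is needed.
- Section 6: the patient is assigned in the interventional suite.
- Section 7 (Entry): the patient is randomised once eligibility and consent are settled; the angiogram is not mentioned.

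What was actually given is recorded. Section 4 lists the number and dose of drug applications among the data collected, and Section 11 says "vasodilator(s) used (Group #) and numbers of the treatment sessions will be submitted via REDCap".

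**The concern.** Analysis by randomised arm is the right primary approach to efficacy. For drug toxicity it has a known weakness. A patient who received no study drug cannot have drug toxicity but still counts in the denominator. A patient given another arm's drug has any resulting event counted under an arm that did not cause it. Both usually pull the arms together. For harm that is the unsafe direction, because it can understate a real excess.

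It matters here because the trial's hypothesis favours the three-drug regimen, and its toxicity relative to a single agent is a natural safety question. With one population and no safety set, the plan has no table that would show whether departures had hidden part of a difference.

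**Working it through.** The plan states no figure on this point, so there is nothing to reproduce. The check has two parts.

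**1. Can departures occur under the text?**

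- Never infused: Section 5 admits symptomatic patients on clinical signs or transcranial Doppler. Need for drug, and the exclusion of patients needing treatment in all three territories, are settled at the angiogram (Section 4). Section 4 delays disclosure to the physician until then but does not say that randomisation itself waits, and Section 7 places randomisation at entry. A patient can therefore be randomised and then not infused.
- Another arm's drug: physicians are unblinded (Section 4), so switching is possible. Repeat sessions must use the same drug (Section 4), which limits it.

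**2. How much would they change the SAE comparison?**

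Inputs from the plan: a maximum of 110 per arm ("A maximum of 330 subjects, 110 per treatment arm, will be randomized") and a 5% level with no multiplicity adjustment. Assumed, because the documents give no values: the drug-related SAE risks and the departure shares.

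Take one single-agent arm with risk p1 and the cocktail arm with risk p2. Let a share u of each arm be never infused, and let a share c of the infused patients in each arm receive the other regimen. Then:

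- reported single-agent risk = (1-u)[(1-c)p1 + c·p2]
- reported cocktail risk = (1-u)[(1-c)p2 + c·p1]
- reported difference = (1-u)(1-2c)(p2 - p1)

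With p1 = 10% and p2 = 20%, a true gap of 10 points:

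| Never infused u | Switched c | Calculation | Reported gap (points) |
|---|---|---|---|
| 0% | 0% | 10 × 1 × 1 | 10.0 |
| 2% | 1% | 10 × 0.98 × 0.98 | 9.6 |
| 5% | 0% | 10 × 0.95 | 9.5 |
| 10% | 0% | 10 × 0.90 | 9.0 |
| 0% | 5% | 10 × 0.90 | 9.0 |
| 0% | 10% | 10 × 0.80 | 8.0 |

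The gap column depends only on the 10-point difference, not on the level of the risks.

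Power does depend on the level. For 10% against 20% at 110 per arm, two-sided 5%, it is 0.55 with no departures, 0.50 with 10% never infused and 0.38 with 10% switching. For 5% against 15% the same three figures are 0.70, 0.65 and 0.51.

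Removing never-infused patients restores the size of the gap but almost none of the power, because the sample shrinks. With 10% never infused, 110 × 0.90 = 99 per arm remain, and power is 0.504 against 0.497 (10% and 20%), or 0.652 against 0.647 (5% and 15%). For non-infusion, the benefit of a safety set is a more accurate estimate.

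**Direction when non-infusion is unequal** (10% against 20%, no switching):

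- 10% never infused in the lower-risk arm only: 20 - 10 × 0.90 = 11 points, wider than the truth.
- 10% never infused in the higher-risk arm only: 20 × 0.90 - 10 = 8 points.

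**The case against.** The strongest reply is that the documents make departures unlikely. The arm is disclosed only after need is confirmed, assignment takes place in the interventional suite (Section 6), repeats use the same drug, and the named rescue is balloon angioplasty, not another arm's drug. Section 10 also expects no missing primary outcome, which presumes that randomised patients are infused. This stands as to size. It does not remove the gap, because Section 7 allows randomisation before the angiogram.

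A reader might infer that the plan expects departures, because it analyses patients whatever they received and because Appendix III lists unauthorised drug use as a major deviation. The documents do not support that. The first is the ordinary definition of intent-to-treat and the second is an entry in a general table of deviation classes.

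The SAE definition in Appendix III is not limited to drug-related events, so never-infused patients are not event-free. The formula applies to the drug-related part only; each arm's total SAE rate falls by less. This stands.

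The safety board classifies serious related events as procedure related, drug related or other (Appendix III). That helps attribution, but it does not settle who is in the denominator or under which regimen an event is counted.

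Finally, grouping by regimen received loses the protection of randomisation. With unblinded physicians, patients given extra agents may be those with the most refractory spasm, and their disease-driven events would move with them. This stands, and it is why the new table should accompany the intent-to-treat table and not replace it.

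**Conclusion.** The point holds as a low-severity omission. One intent-to-treat rule governs the only stated harm comparison, and nothing in the plan would reveal dilution by non-infusion or switching. The size is unknown. On an assumed 10-point drug-related gap the loss is 0.4 points with 2% never infused and 1% switching, and 1.0 point with 10% never infused. It is near zero if departures are near zero. These figures assume departures that are equal in both arms and unrelated to a patient's risk.

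Two stronger readings are tempting and should not be drawn. A reader might infer that the rule necessarily makes the cocktail look safer; unequal non-infusion can widen the gap, so shrinkage is the usual direction and not a certain one. A reader might also infer that all adverse events are analysed this way; only SAEs have a stated analysis. That analysis is exploratory, and the arm-dropping rule in Section 10 uses the primary outcome, not SAEs.

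**What to change.** In the Final Analyses part of Section 10:

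1. Keep intent-to-treat for the post-infusion improvement ratio, the modified Rankin Scale and balloon angioplasty, and keep the intent-to-treat SAE table.
2. Add a safety-set SAE table of all patients who received any intra-arterial study drug, grouped by regimen received. For this table, count a partly delivered cocktail as cocktail, so that an infusion stopped early for a complication is not classed as single-agent. List any other off-protocol combination separately.
3. Report by arm the numbers never infused and the numbers switched.
4. State that grouping by regimen received is not protected by randomisation, and that the two SAE tables are to be read together.

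Separately, reconcile Sections 4, 6 and 7 on when randomisation takes place relative to the diagnostic angiogram.

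The cost is a few sentences and one extra table. The drugs, doses and number of applications are already collected, so no new data are needed.

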A retrospective study⁸ was recently conducted in consecutive patients treated for cerebral vasospasm at The University of Texas Medical School, Memorial Hermann Hospital at the Texas Medical Center, a tertiary treatment center in Houston. Two cohorts were involved. Group 1 (N=47 patients, 116 vessels) was treated between 2008-2011 with a single agent; Group 2 (N=69 patients, 106 vessels) was treated between 2010-2013 with a cocktail of multiple agents (nitroglycerin, verapamil, nicardipine). Patient demographics, age, and modified Rankin score (mRS) at discharge and at 3 months were collected in the cerebrovascular database. Arterial luminal diameters were measured in cerebral angiograms both pre-infusion (PrID) and post-infusion (PoID). The Improvement Ratio (IR) = (PoID - PrID/PrID) x 100 was calculated and statistically compared among groups. This study results showed, Group 2 demonstrated a significantly greater improvement IR 45.8% (SD 36.6) than Group 1 IR 10.9% (SD 12.0), P<0.001. Multiple agent therapy. Comparison of the IR between different single agents within Group 1 (nicardipine and verapamil) demonstrated no difference in vessel diameter change. Patient age had no effect on efficacy in either group.

The conclusion of this study is that treatment of cerebral vasospasm with an IA cocktail of nitroglycerine, verapamil, and nicardipine provides significantly better angiographic improvement of vasospasm than does single agent therapy. (This study has been presented at the International Stroke Conference 2014, in San Diego, CA).

This encouraging result has led us to pursue this proposed prospective evaluation of the efficacy of cocktail drug agent infusion therapy versus the current standard of care single agent therapy that is used by the majority of neuro-interventionists throughout the United States.

The goal of this study is to determine the optimal intra-arterial drug treatment regimen for treating cerebral vasospasm.

Given that each of currently commonly used intra-arterial vasodilators (verapamil, nitroglycerin and nicardipine) has its own mechanisms of action despite some of them belonging to the same drug category ⁹, combining these medications for intra-arterial infusion potentially provides synergistic effects of cerebral vasodilation while minimizing cardiovascular instability induced by high doses of single agent treatment.

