Table 3 demonstrates, that for a hypothesized scenario of "Combo 20" where the combination therapy PIIR is 0.30 compared to 0.10 in Nicardipine and Verapamil, the study will have over 90% power and an expected sample size of 177. Both the Nicardipine and Verapamil arms would have been dropped at interim analyses before they reached their maximum enrollment of 110. If the scenario of "Mixed 1530" is observed, a situation where the Nicardipine arm PIIR is 0.10, the Verapamil arm PIIR is 0.15 and the combination arm is 0.30, the study will have 77% power and an expected sample size of 211. Again, both the Nicardipine and Verapamil arms would have been dropped at interim analyses before they reached their maximum enrollment of 110.

Missing Data and Dropout Rate: We do not anticipate missing data for the primary outcome PIIR as the angiogram will be performed 10 minutes post-infusion. For the secondary outcome, mRS at 3-months, based on previous studies, we estimate up to a 20% loss follow-up. Efforts will be made to keep all patients in the study through the 3-month follow-up visit. Substantial efforts will be made to ensure complete follow-up. Rates of missing data and loss to follow-up will be reported by treatment arm. We will attempt to document maximum amount of information regarding the status of these

patients who drop out. This procedure will help to compare characteristics of those patients who completed the study with those who did not.

Data and Safety Monitoring:

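### The PIIR tests pool one variance at every look, although the only PIIR SDs in the document differ threefold; name Welch/Games-Howell, state the simulation SDs and re-check 0.02 and 0.0330

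*Combined protocol and SAP*

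**What the plan says.** Section 10 (Final Analyses): "At the final analysis, the primary outcome measure, PIIR will be compared between treatment arms using an ANOVA model". If the overall test is significant at 5%, pairwise comparisons follow with Tukey-adjusted p<0.0330. Interim looks use the same pair of tests: "If any pairwise comparison is significant at a Tukey's adjusted two-sided p-value of 0.02 (p< 0.02), the poor performing arm will be dropped". Data from dropped arms stay in the final test.

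On 0.0330 the section says "This value controls global type I error (mistakenly claiming any pairwise difference when all treatments are equal". It ties that value to six interim looks and a two-year accrual period. It names no unequal-variance method, variance check or transformation.

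Section 10 (Sample Size Justification) gives simulated means, power and expected N, but no SD. It says "The simulations focused on the V>N, C>N, and C>V comparisons".

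The only information on the spread of PIIR is in Section 3: "Group 2 demonstrated a significantly greater improvement IR 45.8% (SD 36.6) than Group 1 IR 10.9% (SD 12.0), P<0.001".

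**The concern.** ANOVA and Tukey's test, as usually run, estimate one residual variance and use it for every pair of arms. If the cocktail arm is much more variable than the single-agent arms, that pooled variance is wrong in both directions. At equal arm sizes it is too small for cocktail versus single agent, which inflates false positives. It is too large for nicardipine (N) versus verapamil (V), which hides real differences.

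These tests decide which arm closes, when the trial ends and which regimen is called best, so the error acts at every look. Because neither Table 3 nor 0.0330 comes with an SD, a reader cannot tell whether the plan's own variability data were considered.

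**Working it through.** **Inputs.** The thresholds (0.05 gate, 0.02 interim, 0.0330 final), the 110-per-arm cap, the looks at 40/70/110/165/248 completers and the Table 2 means come from Section 10. The SDs 0.366 (cocktail, C) and 0.12 (single agents) come from Section 3, rescaled from percentages and treated as patient-level (assumption). All other SDs are assumptions.

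**Simulation set-up.** 20,000 trials per cell; normal data; balanced allocation among open arms; dropped arms kept in later tests; no overrun unless stated. Monte Carlo SE is sqrt(0.10 × 0.90 / 20,000) = 0.2 points at 10%. A false claim means one standing at the end of the trial; an interim drop alone is not counted.

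**Step 1: Table 3.** The plan reports expected N 177 and 211, and power 0.95 and 0.77 (Combo 20 and Mixed 1530). With no SD given, this can only be back-solved.

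| SDs N/V/C | Expected N | Power C>V | C beats both |
|---|---|---|---|
| common 0.34 | 180, 215 | 0.96, 0.79 | 0.93, 0.77 |
| 0.30/0.30/0.40 | 176, 211 | 0.95, 0.77–0.78 | 0.91, 0.75 |
| 0.12/0.12/0.366 | 98, 134 | – | – |

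The first two rows fit Table 3 about equally well and the third does not. The planning SDs therefore cannot be recovered, and no conclusion is drawn about which variances were assumed.

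**Step 2: standard errors at 110 per arm.** Pooled MSE = (0.12² + 0.12² + 0.366²)/3 = 0.0543, so the pooled SE is sqrt(2 × 0.0543/110) = 0.0314 for every pair.
- True SE, C versus a single agent: sqrt((0.12² + 0.366²)/110) = 0.0367. The pooled value is 14% too small.
- True SE, N versus V: sqrt(2 × 0.12²/110) = 0.0162. The pooled value is 94% too large.
- At 0.24/0.24/0.366 the pooled SE is 0.0389, against 0.0417 and 0.0324 (7% too small, 20% too large).
- At 0.30/0.30/0.40 it is 0.0454, against 0.0477 and 0.0405 (5% too small, 12% too large).

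These are equal-n figures. Once single-agent arms close early, the pooled SE for the cocktail comparison can be nearly right or too large.

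**Step 3: equal means, false claims.** Ranges are over 2 to 4 random seeds.

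| SDs N/V/C | ANOVA + Tukey | Welch + Games-Howell |
|---|---|---|
| 0.12/0.12/0.366 | 10.3–10.6% | 5.5–5.9% |
| 0.18/0.18/0.366 | 8.1–8.4% | 5.5–5.7% |
| 0.24/0.24/0.366 | 6.4–6.9% | 5.5–5.9% |
| 0.30/0.30/0.40 | 5.8–6.3% | 5.4–6.0% |
| common 0.34 | 5.3–5.8% | 5.4–6.0% |

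With the Section 3 SDs the cocktail is wrongly dropped in 5.5–5.8% of trials, against 1.9–2.1%. Separately coded repeats on this schedule gave false-claim rates of 9.9–11.0% against 5.6–6.0%.

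**Step 4: schedule.** The text gives more than one look schedule, counts six interims where the completer list has five before 330, and says "Enrollment will continue while the interim analyses are performed". Section 11 counts a completer only after 90-day follow-up. At constant accrual the overrun is 330/18 × 3 = 55 or 330/24 × 3 = 41 patients. False claims:

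| Schedule | Section 3 SDs: planned, swap | Common 0.34: planned, swap |
|---|---|---|
| six looks (90 added) | 11.1%, 5.9% | 5.8%, 5.9% |
| looks starting at 90 | 8.7%, 4.9% | 5.1%, 5.2% |
| overrun 41–55 | 7.5–8.2%, 4.0–4.2% | 4.1–4.3%, 4.2–4.4% |

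A repeat with six interims spaced evenly from 90 to 290 gave 8.5% against 5.1% with the Section 3 SDs, and 5.0% for both methods with equal SDs. Absolute rates move with the schedule; the gap stays at about 3.5 to 5 points.

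**Step 5: V>N shown in Mixed 1530 (0.10 versus 0.15), planned tests against the swap.**
- Section 3 SDs: 0.1–0.2% against 30% (repeats: 0.0–0.1% against 25–26%); with overrun, 0.2–0.3% against 40–43%.
- SD equal to 0.8–1.1 times each arm's mean: 0.2–0.5% against 21–25%.
- 0.24/0.24/0.366: 1.7% against 7.8%.
- 0.30/0.30/0.40: 2.5% against 5.9–6.3%.
- Common 0.34: 4.6% against 4.5–4.7%.

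**Step 6: other remedies.** A log-ratio scale narrows the gap but does not close it. Under a lognormal assumption, sqrt(ln(1 + (SD/(1 + mean))²)) gives 0.108 and 0.247, still 2.3-fold, with false claims of 9.2% against 5.8%. Tightening thresholds alone would mean cutting both to 0.3 times (0.006 and 0.0099) for about 5% under the Section 3 SDs. C-V power in Mixed 1530 then falls from 79% to 64% (common 0.34) or from 77% to 63% (0.30/0.30/0.40).

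**The case against.** **The type I harm needs equal means with unequal SDs.** In Section 3 the larger SD goes with the larger mean: 36.6/45.8 = 0.80 and 12.0/10.9 = 1.10. If spread follows response, equal means imply similar SDs and global error is not inflated. Read as identical distributions, the plan's claim about 0.0330 is then sound. This stands for type I error. It does not rescue V versus N, where the loss persists with SD proportional to the mean.

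**The SD ratio is fragile.** The source cohorts are retrospective and largely non-concurrent, the SD unit is unstated, and one SD covers both single agents. Vessels per patient were 116/47 = 2.47 and 106/69 = 1.54. If the SDs describe patient averages over independent vessels, averaging alone could account for a factor of sqrt(2.47/1.54) = 1.27, reducing the ratio from 3.05 to about 2.4. This stands, though at a ratio near 2 (single-agent SD 0.18) the planned tests still give 8.1–8.4% without overrun.

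**With overrun, moderate gaps do little damage.** The planned tests give 4.8–5.1% at 0.24/0.24/0.366 and about 4.6% at 0.30/0.30/0.40. This stands; only large SD gaps clearly break 5%.

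**V versus N is not what the trial is powered for.** Section 10 treats C versus V as the leading comparison, and Table 3 gives no V-N power. That limits the weight of Step 5. Still, the plan says every pair will be compared and lists V>N among the comparisons simulated. Early closing of arms ("Both the Nicardipine and Verapamil arms would have been dropped at interim analyses before they reached their maximum enrollment of 110") is a further limit under either method.

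**The swap is not better everywhere.** With skewed data (gamma, skewness 1.4), equal means and no overrun, false claims are 5.7% planned against 6.5% swapped at 0.30/0.30/0.40, and 4.8% against 6.2% at equal SDs. Under the Section 3 SDs they are 13.9% against 8.6%. So the swap is about 1 point worse when SDs are close, and does not by itself guarantee 5%. This stands, and is why the thresholds need re-checking.

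**Conclusion.** The concern holds and should be fixed, with moderate confidence. The planned tests pool one variance in standard form (inferred from the method names, since no variance structure is written), and the document's sole variability data suggest but do not establish unequal variances.

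If means are equal and SDs are as in Section 3, false claims roughly double and the cocktail is wrongly dropped about three times as often. If variances are equal under the null, there is no type I harm. The loss for V versus N in Mixed 1530 does not depend on equal means. Power for C versus V is not threatened by the planned tests.

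The sizes rest on normal data, patient-level SDs and an assumed look schedule. Whatever the true SDs, the missing simulation SDs leave Table 3 and the 0.0330 claim uncheckable. This is a low-cost gain in robustness, not a flaw that invalidates the design.

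**What to change.** 1. At each interim look and at the final analysis, use Welch's ANOVA (p<0.05) as the gate and Games-Howell pairwise p-values in place of Tukey's.
2. State the SDs used for Table 3 and for 0.0330.
3. Re-run the simulations on the actual look schedule, including patients enrolled while earlier ones complete follow-up. Cover equal SDs, an intermediate set (for example 0.24/0.24/0.366 or 0.30/0.30/0.40), the Section 3 SDs and a skewed distribution.
4. Confirm or reset 0.02 and 0.0330 and restate Table 3 before use. As an illustration, Games-Howell with both thresholds at 0.85 times (0.017 and 0.028) gave 4.5–5.0% in all three cases tried (Section 3 SDs, 0.30/0.30/0.40, common 0.34). C-V power in Mixed 1530 was 77% at common 0.34 and 73% at 0.30/0.30/0.40.

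The work is SAP wording and one simulation re-run; the 330 maximum is unchanged. The price of the swap at the present thresholds is:

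| SDs N/V/C | Expected N, Combo 20 | Expected N, Mixed 1530 | C-V power, Mixed 1530 |
|---|---|---|---|
| 0.12/0.12/0.366 | 98 to 128 | 134 to 166 | 96.5% to 94.3% |
| 0.30/0.30/0.40 | 176 to 190 | 211 to 223 | 77–78% to 75% |
| common 0.34 | 180 to 183 | 215 to 217 | 79% to 78–79% |
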